7.10.5 Physical Examination

Abnormalities found in physical examinations will be listed at each scheduled visit for physical examination.

7.10.6 12-lead *Electrocardiogram (ECG)*

Number and percentage of subjects with normal/abnormal and clinically significant abnormal ECG findings will be summarized at each scheduled visit for 12-lead ECG.

A listing for 12-lead ECG will be provided.

7.10.7 *Pregnancy Test*

A listing of all pregnancy tests results will be provided.

7.11 *Palatability Assessments*

In children \geq 6 years old, patiromer palatability assessments (taste and overall liking) will be summarized using descriptive statistics. A 5-point scale for taste and overall liking includes dislike very much, dislike somewhat, neither like nor dislike, like somewhat, and like very much.

For children $<$ 6 years old, assessment of the subject's parental acceptance of patiromer will be summarized using descriptive statistics. A 5-point agreement/disagreement scale to a statement of the subject's ($<$ 6 years of age) acceptance of patiromer includes strongly disagree, somewhat disagree, neither agree nor disagree, somewhat agree, and strongly agree.

Appendix A: Schedule of Events (Screening and Pharmacodynamic / Dose Finding Phase)

Study Activity	Phase	Screening		Pharmacodynamic / Dose Finding Phase			ET ^b	MSV ^c
		Subject With Standard of Care Potassium	Subject Without Standard of Care Potassium	D3 ^a (± 1d)	D7 (± 3d)	D14 (± 3d)		
	Scenario	Visit	SV1/D1	SV2/D1 (2 to 7 days after SV1)				
Informed Consent		X	X					
I/E Criteria		X		X				
Demographics		X	X					
Medical History		X	X ^d					
Physical Examination		X	X ^d				X	X
Body Weight		X		X			X	X
Height		X	X ^d				X	X
Vital Signs (Resting Heart Rate and Sitting BP)		X	X	X	X	X	X	X
12-Lead ECG		X	X ^d		X ^m	X ^m	X ^m	X ^l
Potassium		L&C ^e	L	L&C ^e	L&C	L&C	L&C	L&C
Chemistry ^f		L&C ^e		L&C ^e		C	C	C
Hematology (CBC)		L&C ^e		L&C ^e			C	C
Plasma Parathyroid hormone		C ^e		C ^e			C	C
Serum Fluoride		C ^e		C ^e			C	C
Urinalysis ^g		C ^e		C ^e			C	C
Pregnancy Test ^h		L&C ^e		L&C ^e				L&C
IWRS Entry		X	X	X	X	X	X	X
Patiromer Administration ⁱ		X ^e		X ^e	X ^j	X	X	
Patiromer Palatability and Parental Assessment ^k		X ^e		X ^e			X	

Appendix A: Schedule of Events (Screening and Pharmacodynamic / Dose Finding Phase) (Cont'd)

Study Activity	Phase	Screening		Pharmacodynamic / Dose Finding Phase			ET ^b	MSV ^c
	Scenario	Subject With Standard of Care Potassium	Subject Without Standard of Care Potassium	D3 ^a (± 1d)	D7 (± 3d)	D14 (± 3d)		
	Visit	SV1/D1	SV1	SV2/D1 (2 to 7 days after SV1)				
Dosing Diary Dispensation		X		X				
Dosing Diary Review by Investigator/Designee					X	X	X	
Dosing Diary Collection							X	
Drug Accountability & Compliance		X ^c		X ^c	X	X	X	X
AE Assessment	X	X	X	X	X	X	X	X
Con Meds Assessment	X	X	X	X	X	X	X	X

AE = Adverse Event; ALT = alanine aminotransferase; AST = aspartate aminotransferase; C= Central; D = Day; d = day/days; Laboratory; CBC = Complete Blood Count; Con Meds = concomitant medications; E = exclusion; ET = Early Termination; ECG = Electrocardiogram; eGFR = Estimated Glomerular Filtration Rate; I = inclusion; IWRS = Interactive Web Response System; L= Local Laboratory; SV1= Screening Visit 1; SV2 = Screening Visit 2 (2 to 7 days after SV1); W = Week

- ^a Note: At the discretion of the Investigator, the Day 3 Visit is optional for subjects whose last screening K^+ is < 5.5 mEq/L; for subjects whose last screening K^+ is ≥ 5.5 mEq/L, the Day 3 Visit is mandatory (see Section 6.2.2)..
- ^b After ET subjects should be encouraged to complete the Follow-up Period Visits (see Section 6.4).
- ^c Or any unscheduled visit.
- ^d Assessment may be performed either on SV1 or SV2.
- ^e Central laboratory measurement or event will not be performed unless subject meets study entry criteria.
- ^f For screening, local hematology (CBC including WBC, RBC, hemoglobin, hematocrit, and platelet count) will be performed. Per Investigator's decision, central laboratory assessment of calcium and/or phosphate levels may be tested more frequently for subjects that have one dose of phosphate binder replaced by patiromer.
- ^g Not required for anuric subjects; see Section 7.2 for details.
- ^h Female subjects of child bearing potential only. For anuric subjects, a serum pregnancy test is required; please Section 7.2 for details.
- ⁱ If patiromer dose requires titration, then initiation of the titrated patiromer dose should occur at the next planned administration (see Section 5.2.1 for details)
- ^j Up-titration of patiromer can occur only if the K^+ level is ≥ 5.5 mEq/L and greater than the most recent locally obtained screening potassium value.
- ^k Palatability of patiromer will be evaluated in children ≥ 6 years of age when the initial dose is administered at the study site on Day 1 and parental or legal authorized representative response on the subject's (< 6 years of age) acceptance of patiromer will be assessed on Day 14 (see Section 7.6 for further details).
- ^l ECG at the Mandatory Safety Visit required only if the local potassium is >6.0 mEq/L at the current or prior visit (see [Section 6.5.1](#))
- ^m ECG is only required if the local potassium is > 6.0 mEq/L

Appendix B: Schedule of Events (Long-Term Treatment Phase)

Study Activity	Study Period	Long-Term Treatment Phase								F1 7d ± 3d	F2 ^a 14d ± 3d	ET	MS V ^b
		W3 ⁱ ± 3d	W5 ± 7d	W7 ± 7d	W10 ⁱ ± 7d	W14 ± 7d	W18 ± 7d	W22 ⁱ ± 7d	W26 ± 7d				
Visit													
Informed Consent													
I/E Criteria													
Demographics													
Medical History													
Physical Examination ^k			X		X				X			X	
Body Weight ^k			X		X				X			X	
Height ^k			X		X				X			X	
Vital Signs (Resting Heart Rate and Sitting BP)	X	X	X	X	X	X	X	X	X			X	X
12-Lead ECG ^c	X ^l	X ^l	X ^l	X ^l	X ^l	X ^l	X ^l	X	X ^l			X	X ^j
Potassium	L & C	L& C	L & C	L& C	L& C	L & C	L& C	L& C	L&C			L& C	L& C
Chemistry ^e			C		C			C	C			C	
Hematology (CBC)			C		C			C				C	
Plasma Parathyroid hormone								C				C	
Serum Fluoride			C		C			C				C	
Urinalysis ^f								C				C	
Pregnancy Test ^g									L& C			L& C	
IWRS Entry	X	X	X	X	X	X	X	X	X	X	X	X	X

Appendix B: Schedule of Events (Long-Term Treatment Phase) (Cont'd)

Study Activity	Study Period	Long-Term Treatment Phase									F1 7d ± 3d	F2 ^a 14d ± 3d	ET	MSV ^b
		W3 ⁱ ± 3d	W5 ± 7d	W7 ± 7d	W10 ⁱ ± 7d	W14 ± 7d	W18 ± 7d	W22 ⁱ ± 7d	W26 ± 7d					
Visit														
Patiromer Administration ^h	X	X	X	X	X	X	X							X
Drug Accountability & Compliance	X	X	X	X	X	X	X	X					X	X
AE Assessment	X	X	X	X	X	X	X	X	X	X	X	X	X	X
Con Meds Assessment	X	X	X	X	X	X	X	X	X	X	X	X	X	X

AE = Adverse Event; ALT = alanine aminotransferase; AST = aspartate aminotransferase; d = days; C= Central Laboratory; CBC = Complete Blood Count; Con Meds = concomitant medications; E = exclusion; ET = Early Termination; ECG = Electrocardiogram; eGFR = Estimated Glomerular Filtration Rate; F1 = Follow-up Visit 1 at 7 Days (± 3 days) after the last dose of patiromer; F2 = Follow-up Visit 2 at 14 Days after the last dose of patiromer; I = inclusion; IWRS = Interactive Web Response System L= Local Laboratory; M = months; MSV = Mandatory Safety Visit; W = week

- ⁿ The Phone Call Follow-up may be converted into an Onsite Visit if potassium levels from F1 is of concern by the Investigator and require a re-test. If subjects are requested to return for an onsite visit, the same activities will be performed as those in (F1)
- ^o Or any unscheduled visit
- ^p When K⁺ is > 6.0 mEq/L during the Long-Term Treatment Phase of the study, additional ECG evaluations will be performed.
- ^q Per Investigator's decision, central laboratory assessment of calcium and/or phosphate levels may be tested more frequently for subjects that have one dose of phosphate binder replaced by patiromer.
- ^r Not required for anuric subjects, see Section 7.2 for details.
- ^s Female subjects of child bearing potential only. For anuric subjects, a serum pregnancy test is required; see Section 7.2 for details.
- ^t If patiromer dose requires titration, then initiation of the titrated patiromer dose should occur at the next planned administration (see Section 5.2.1 for details).
- ^u The last dose of patiromer will be taken the day before the Week 26 Visit.
- ^v Week 3, Week 10 and Week 22 visits may be skipped under specific conditions (See Section 3.2.3)
- ^w ECG at the Mandatory Safety Visit required only if the local potassium is >6.0 mEq/L at the current or prior visit (see Section 6.5.1)
- ^x Study activity may be omitted for Home Care visit (see Section 6.2.5)
- ^y ECG is only required if the local potassium is > 6.0 mEq/L

Appendix C: Missing Data Imputation

1 Imputation of Missing/Partially Missing Adverse Event Dates

1.1 Incomplete Start Date

Partially missing AE start/stop dates will be imputed in the ADaM dataset for AEs, according to the rules below. However, listings of AE data will present the date as is, with missing date components left blank.

If the AE end date is complete with no missing year, month, or day, and a partially missing start date imputed by the rules below is after the AE end date, then the imputed start date will be equal to the end date.

Missing day and month

- If the year is the **same** as the year of the first dosing date, then the day and month of the first dosing date will be assigned to the missing fields.
- If the year is **prior to** the year of first dosing date, then December 31 will be assigned to the missing fields.
- If the year is **after** the year of first dosing, then January 1 will be assigned to the missing fields.

Missing day only

- If the month and year are the **same** as the year and month of first dosing date, then the first dosing date will be assigned to the missing day.
- If either the year of the partial date is **before** the year of the first dosing date or the years of the partial date and the first dosing date are the same but the month of partial date is **before** the month of the first dosing date, then the last day of the month will be assigned to the missing day.
- If either the year of the partial date is **after** the year of the first dosing date or the years of the partial date and the first dose date are the same but the month of partial date is **after** the month of the first dosing date, then the first day of the month will be assigned to the missing day.

Missing day, month, and year

- No imputation is needed. The corresponding AE will be included as TEAE.

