8.2 Procedures for Eliciting, Recording and Reporting Adverse Events

8.2.1 Adverse Event Reporting Period

AEs, including SAEs, will be collected throughout the study period, beginning from the time the ICF is signed until the subject's last study visit (normally the last follow-up visit). Any AE or SAE will be followed until it resolves or becomes stable. The Investigator must report any AEs that occur after the protocol specified reporting period if according to the Investigator's assessment there was a reasonable possibility that the AE was related to patiromer or any study procedures.

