9.5 Safety Analysis

Safety variables will include:

- All AEs
- SAEs
- Clinical laboratory test results
- Vital signs

- ECG
- Deaths
- Reasons for dosing interruption or discontinuation
- Laboratory safety summaries will include:
 - Incidence of potassium (1) < 3.0 mEq/L, (2) < 3.5 mEq/L, (3) ≥ 5.1 mEq/L and (4) ≥ 5.5 mEq/L (measured by central laboratory)
 - Incidence of serum magnesium (1) < 1.4 mg/dL (< 0.58 mmol/L), (2) < 1.2 mg/dL (< 0.49 mmol/L) and (3) < 1.0 mg/dL (< 0.41 mmol/L) (central laboratory)
 - Calcium levels, phosphate levels, and serum fluoride levels will be assessed based on central laboratory analysis of samples collected at each of the scheduled study visits

The analysis of treatment-emergent AEs will include all events with onset or worsening on or after the date of first dose of patiomer.

Complete details of the safety analyses will be presented in the SAP.

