7.10 Safety Analyses

7.10.1 Adverse Events

AEs and SAEs will be coded to system organ class (SOC) and preferred term (PT) with the latest available MedDRA. Adverse event analyses will include only treatment-emergent AEs (TEAEs). A TEAE is defined as any AE that newly appeared or worsened in severity following initiation of study drug administration. If the onset date of an AE is missing, the AE will be considered treatment-emergent unless there is evidence to conclude that it is not. AE listings will include all AEs.

The incidence of TEAEs will be summarized by system organ class (SOC), preferred term (PT) and severity. For those TEAEs that occur more than once during the study period, the maximum severity will be used in the summary by severity.

Descriptive statistical summaries (frequencies and percentages) will be provided for the followings:

- Overall summary of number of subjects with: any TEAE; any TEAE related to study drug; any SAE; any SAE related to study drug; any TEAE leading to study drug dose increase, dose reduction, dose interruption; any TEAE leading to study drug discontinuation
- Summary of all TEAEs by SOC, PT and severity
- Summary of TEAEs related to study drug by SOC and PT
- Summaries of TEAEs leading to study drug dose increase, dose reduction, and interruptions by SOC and PT
- Summary of TEAEs leading to early study drug discontinuation by SOC and PT
- Summary of SAEs by SOC, PT, and severity
- Summary of SAEs related to study drug by SOC and PT
- Summaries of TEAEs of special interest (e.g. allergic reactions, gastrointestinal events, renal events)

A listing for all AEs will be provided, including verbatim term, PT, SOC, severity, whether serious, relationship to study drug, onset and end date, action taken, and outcome of event will be provided. A listing of SAEs and TEAEs leading to any study drug modification or discontinuation (increase, reduction, interruption or discontinuation) will also be provided. In addition, listings will be provided for events of special interest.

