1.2 Incomplete Stop Date

If the imputed stop date is before the start date, then the imputed stop date will be equal to the start date.

Missing day and month

- If the year of the incomplete stop date is the **same** as the year of the last dosing date, then the day and month of the last dosing date will be assigned to the missing fields.
- If the year of the incomplete stop date is **prior to** the year of the last dosing date or prior to the year of the first dosing date, then December 31 will be assigned to the missing fields.
- If the year of the incomplete stop date is **prior to** the year of the last dosing date but is the same as the year of the first dosing date, then the first dosing date will be assigned to the missing date.
- If the year of the incomplete stop date is **after** the year of the last dosing date, then January 1 will be assigned to the missing fields.

Missing day only

- If the month and year of the incomplete stop date are the **same** as the month and year of the last dosing date, then the day of the last dosing date will be assigned to the missing day.
- If either the year of the partial date is **not equal to** the year of the last dosing date or the years of the partial date and the last dosing date are the same but the month of partial date is **not equal to** the month of the last dosing date, then the last day of the month will be assigned to the missing day.

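### SAP Appendix C 1.1 counts every adverse event with a wholly missing start date as treatment-emergent, without the contrary-evidence condition of SAP 7.10.1, so an event recorded as ending before the first dose would be counted

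*SAP*

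**What the plan says.** **Which events are collected.** Protocol 8.2.1 collects adverse events "beginning from the time the ICF is signed", so events before dosing are in the database.

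**What counts as treatment-emergent.** Protocol 9.5 says the TEAE analysis "will include all events with onset or worsening on or after the date of first dose of" patiromer. SAP 7.10.1 says: "A TEAE is defined as any AE that newly appeared or worsened in severity following initiation of study drug administration".

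**Missing onset, SAP body.** SAP 7.10.1: "If the onset date of an AE is missing, the AE will be considered treatment-emergent unless there is evidence to conclude that it is not". SAP 6.1 attaches the same condition to an onset that falls on the first dosing date.

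**Missing onset, Appendix C.** SAP 6.2 sends the reader to Appendix C for the specific date rules. For a start with no day, month or year, Appendix C 1.1 says: "No imputation is needed. The corresponding AE will be included as TEAE". The same section sets an imputed start back to the event's end date if it would otherwise fall later. That cap needs a partially missing start and a complete end date.

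**Stop dates.** Appendix C 1.2 says: "If the imputed stop date is before the start date, then the imputed stop date will be equal to the start date". For a stop known only by year, its second bullet assigns 31 December if the stop year precedes the last-dose year or the first-dose year. Its third bullet assigns the first dosing date if the stop year is prior to "the year of the last dosing date but is the same as the year of the first dosing date".

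**The concern.** The clearest evidence that an undated event is not treatment-emergent is a recorded stop date before Day 1. SAP 7.10.1 leaves room for that evidence; the matching line of Appendix C 1.1 does not. A programmer working from Appendix C, where SAP 6.2 points, would count the event. The drafters evidently foresaw the problem, since they wrote a cap at the end date, but the cap stops short of the wholly missing start. Classification then depends on whether someone happened to record the start year.

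At stake is a pre-treatment event appearing in the TEAE tables under a starting dose, in a study that tabulates by age cohort and starting dose and opens each dose level with three children. The potassium endpoints are not involved.

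**Working it through.** No figure in the plan is in dispute, so the check applies the date rules literally to test records. The calendar dates are assumptions chosen for illustration.

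**1. Start-date rules**

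| Case | First dose | Recorded start | Recorded stop | Appendix C 1.1 result | SAP body (7.10.1, 6.1) |
|---|---|---|---|---|---|
| a | 10 Apr 2019 | none | 8 Apr 2019 | TEAE, no condition | Not TEAE: the stop date is contrary evidence |
| b | 10 Apr 2019 | 2019 | 8 Apr 2019 | Start imputed 10 Apr, capped to 8 Apr: before dosing | Agrees |
| c | 10 Apr 2019 | Apr 2019 | 8 Apr 2019 | Start imputed 10 Apr, capped to 8 Apr: before dosing | Agrees |
| d | 3 Sep 2019 | 2019 | Aug 2019 | Start imputed 3 Sep; cap not applicable because the stop is incomplete | 6.1 still allows the recorded stop month as contrary evidence |

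Cases a and b differ only in whether the start year was recorded, yet Appendix C classifies them differently. Case a is the direct conflict. In case d the stop is first imputed as 31 Aug (last day of the month) and then moved forward to 3 Sep by the stop-before-start rule. The derived dates are wrong, but Appendix C does not itself declare that event a TEAE.

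**2. How often this could happen**

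- With a standard-of-care potassium (Protocol 6.1 and 6.1.1): consent is at Screening Visit 1, which becomes Day 1 or is followed by Day 1 the next day. Gap: 0 to 1 day.
- Without one (Protocol 6.1 and 6.1.2): Screening Visit 2 is 2 to 7 days after Screening Visit 1, and Day 1 is the same or the next day. Gap: 2 to 7 + 1 = 8 days.
- Overall, about 0 to 8 days, counting from the consent that led to dosing.
- Case d also needs the event to end in the calendar month before dosing but after consent. If the first dose is on day *k* of a month, consent is no earlier than day *k* − 8, so this needs *k* − 8 ≤ 0, that is, a first dose on days 1 to 8.

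**3. Size if it happens once**

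Group sizes are from SAP 2.3; the display by age cohort, starting dose and overall is from SAP 7.1. For one child with no other event counted in that row, the shift is 1/*n*:

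- *n* = 3: 1/3 = 33 percentage points
- *n* = 12: 1/12 = 8 points
- overall, *n* = 36 to 54: 1/36 = 2.8 down to 1/54 = 1.9 points

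**4. Stop-date bullets (Appendix C 1.2)**

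Take stop year 2018, first dose 1 Oct 2018, last dose 31 Mar 2019. The second bullet gives 31 Dec 2018 and the third gives 1 Oct 2018, 91 days apart; both conditions are met. With 182 days of dosing, 181 of 365 possible first-dose dates (49.6%) cross a year end, so that an event could meet both bullets.

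The gap shrinks when the event starts on treatment. With first dose 3 Sep 2019, event start 10 Oct 2019 and last dose 2 Mar 2020, the third bullet's 3 Sep is reset to 10 Oct. The gap to 31 Dec is then 82 days, not 119.

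**The case against.** The best defence is that Appendix C merely abbreviates SAP 7.10.1. TEAE status is defined in the body, an event that ended before dosing fails that definition, and the appendix only handles dates. That is a reasonable guess at intent. But the Appendix C line does assign TEAE status, it omits the condition, and the SAP gives no precedence between its body and its appendix.

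The defence on rarity stands. The record needs a known pre-dose stop and not even a start year, inside a window of about 8 days. Sites ask about events at each screening visit, onset and resolution dates are captured (Protocol 8.2.5), and incomplete data are queried (Protocol 10.1).

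A reader might infer from case d that the SAP also forces such events into the TEAE tables and destroys the evidence against them. The documents do not support that. Appendix C only assigns a date there, SAP 6.1 still applies its condition to an onset on the first dosing date, and the listings keep the recorded partial dates.

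A reader might also infer from the stop-date overlap that results would change materially. They would not: no table planned in SAP 7.10.1 uses event duration or the imputed stop date. The third bullet could be meant as an exception to the second. Dosing lasts about 6 months, so that reading leaves the second bullet's last-dose clause with nothing to do, but redundancy is not contradiction. Nor do the documents say that 31 December is the intended date.

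**Conclusion.** The conflict between Appendix C 1.1 and SAP 7.10.1 is real and is confined to events with a wholly missing start and a stop date, complete or partial, that lies before the first dose. Followed literally, Appendix C counts such an event as treatment-emergent. The documents cannot show how many such records will exist; the short interval from consent to dosing makes none or very few likely. The 33-point and 8-point shifts are what one such child would do to a single row, not an expected bias.

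Two lesser matters are consistency corrections only: derived dates that disagree with the recorded stop when both dates are partial (case d), and the overlapping year-only stop bullets. The 49.6% assumes first doses spread evenly over the year and full 26-week dosing, and it counts children who could be affected, not events with year-only stops. Overall this is a low-priority clarification, worth making because it is cheap.

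**What to change.** Before database lock, amend SAP Appendix C:

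1. In 1.1, for a wholly missing start, replace the last line with: *included as TEAE unless the recorded stop date, complete or partial, shows the AE ended before the first dose*.
2. In 1.1, let the start-date cap also use a partial stop date, taken as the latest date its recorded parts allow. Case d then gets a start of 31 Aug 2019, in line with SAP 6.1 and 7.10.1. The start no longer falls after the stop, so the stop is not moved forward and 1.2 needs no further change for this purpose.
3. In 1.2, make the second and third year-only bullets mutually exclusive, with the sponsor stating which date is intended when the stop year is the first-dose year and precedes the last-dose year.

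The cost is a few lines of SAP text and minor programming. No data collection or planned table changes.
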